# 6.8 Analysis of Primary Endpoints

The co-primary endpoints are the change from baseline to 12 weeks in ADAS-Cog11 scores and the ADCS-CGIC scores at 12 weeks. The ADAS-Cog11 will be analyzed via mixed models for repeated measures (MMRM). The model for ADAS-Cog11 will include treatment, timepoint, treatment-by-timepoint interaction as the fixed effects, baseline ADAS-Cog11as the covariate, and subjects as random effect. The Model for ADCS-CGIC will include treatment, timepoint, treatment-by-timepoint interaction as the fixed effects, and subjects as random effect. An unstructured covariance matrix will be used and the Kenward-Roger approximation will be used to adjust the denominator degrees of freedom. The change from baseline and the differences in the change from baseline between treatments will be based on the Least Square Means from this model. The two-sided 95% confidence intervals of the treatment differences will be presented.

Ver. 3.1; 09-25-2023

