Participants who have signed an informed consent and meet screening eligibility requirements will be randomly assigned at a 1:1:1:1 ratio to one of the four treatment arms: buntanetap 7.5 mg, buntanetap 15 mg, buntanetap 30 mg, and placebo, through an Interactive Randomization System, after a screening period of up to 42 days, followed by an at home dosing period of 12 weeks. Participants will be required to visit clinics at Day 0 (baseline), 6 weeks, and 12 weeks (end-of-trial), where they will undergo study procedures that include safety assessments (AE and concomitant medication monitoring, 12-lead ECGs, clinical laboratory testing, vital signs assessments, and physical/neurological examinations), and psychometric tests (ADAS-Cog11, ADCS-CGIC, ADCS-ADL, DSST, MMSE).

The Schedule of Events is shown in Appendix 1.

6 Determination of Sample Size

A sample size of up to 320 participants (1:1:1:1 randomized to 7.5 mg, 15 mg, 30 mg buntanetap and placebo respectively) is planned to be randomized.

Qualified participants will be randomized at a 1:1:1:1 ratio to one of the following four treatment groups: 7.5 mg, 15 mg, 30 mg QD buntanetap and placebo. A sample size of 280 (210 combining all three buntanetap-treatment groups and 70 in control) will have 90% power to detect a treatment difference for the co-primary efficacy variable ADAS-Cog11 at a two-sided significance level of 0.05, assuming a delta of 2.7 between the treatment (pooling all three treatment arms together) and placebo, and a common standard deviation (SD) of 6.0. This sample size will also have an 89% power to detect a significant difference for the co-primary efficacy variable ADCS-CGIC at a two-sided significance level of 0.05, assuming a delta difference 0.23 between the treatment (pooling all three treatment arms together) and placebo, and a common SD of 0.5. Approximately 320 participants will be randomized (approximately 80 per arm) to account for an expected 12.5% dropout rate.

7 Data Sets to be Analyzed

The following analysis sets will be used for the statistical analysis and presentation of data:

- The Enrolled analysis set (ES) will include all participants who signed IC and meet all inclusion
 and exclusion criteria. All data collected from ES will be presented in listings and if relevant in
 tables and/or graphs. Screening failures will have selected data be presented in a separate
 listing if needed.

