8.2.3 Summary Statistics

Data will be summarized by means of summary statistics. Summary statistics will be provided for the variables described in the following sections.

Categorical data will be presented as counts and percentages, i.e., n (xx.x%). Percentages will be based on the number of subjects in the analysis data set used and given as integers. Zero frequencies will be given without percentages.

For continuous variables, these statistics will include the number of subjects, mean, SD, median, minimum, and maximum.

All variables will be analyzed descriptively with appropriate statistical methods: categorical variables by frequency tables (absolute and relative frequencies) and continuous variables by sample statistics (i.e., number of observations, mean, SD, 95% CI of the mean, minimum, median, first and third quartiles and maximum). Minimum and maximum values will be displayed as reported.

Since the two co-primary endpoints and secondary endpoints are captured at multiple visits, the method selected to analyze the endpoints, which are treated as continuous, will be a Mixed Model for Repeated Measures (MMRM). For the co-primary endpoint ADAS-Cog11 score and secondary endpoints, MMRM will be applied with change from Baseline score as the response (dependent variable) and with Baseline value as a covariate and treatment, timepoint, treatment-by-timepoint interaction as fixed effects (independent variables). The Model for co-primary endpoint ADCS-CGIC score will include treatment, timepoint, treatment-by-timepoint interaction as the fixed effects. Estimation of parameters will be done by means of Restricted Maximum Likelihood method. The Unstructured (UN) variance-covariance structure will be initially used to explore the variance-covariance matrix across visits. If the algorithm doesn't converge, a heterogeneous Toeplitz (TOEPH) as the covariance matrix will be tried first, and then first-order autoregressive (AR(1)) to achieve convergence. The Kenward-Roger approximation will be used to estimate denominator degrees of freedom. The two-sided 95% CI of the treatment differences will be presented.

The co-primary endpoint ADAS-Cog11 score and secondary endpoints will be analyzed using the model explained above as follows:

```
<Endpoint>= intercept + Base + T + V + T*V,
```

with

Base: baseline score;

T: treatment;

V: post-baseline visit (Week 6, Week 12).

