The co-primary endpoint ADCS-CGIC score will be analyzed using the model explained above as follows:

<Endpoint>= intercept + T + V + T*V,

with

T: treatment;

ANVS-22002

V: post-baseline visit (Week 6, Week 12).

Treatment comparisons (pooled Buntanetap-treatment vs. Placebo) will be carried out by means of the contrasts on the treatment factor by visit effect in SAS® Software, using proc mixed. Treatment effects will be estimated by means of Least Square Means (LSM) and 95% CI. Differences between treatments (pooled Buntanetap-treatment – Placebo) will be estimated and resulting 2-sided p-values and associated 95% CI will be presented.

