8.2.7 Primary Analysis

The co-primary endpoints in this clinical trial are the change from baseline to Week 12 in ADAS-Cog11 score and the ADCS-CGIC score at Week 12 between buntanetap-treatment (pooling three treatment arms together) and placebo.

The statistical hypothesis to be tested for co-primary endpoint ADAS-Cog11 score is described as:

• Null Hypothesis (H0):

The difference in change in ADAS-Cog11 score from baseline to Week 12 between buntanetap-treatment (pooling three treatment arms together) and placebo = 0.

Alternative Hypothesis (H1):

The difference in change in ADAS-Cog11 score from baseline to Week 12 between buntanetap-treatment (pooling three treatment arms together) and placebo $\neq 0$.

The statistical hypothesis to be tested for co-primary endpoint ADCS-CGIC score is described as:

Null Hypothesis (H0):

The difference in ADCS-CGIC score at Week 12 between buntanetap-treatment (pooling three treatment arms together) and placebo = 0.

Alternative Hypothesis (H1):

The difference in ADCS-CGIC score at Week 12 between buntanetap-treatment (pooling three treatment arms together) and placebo $\neq 0$.

The two co-primary endpoints will be analyzed via MMRM. The model for the co-primary endpoint ADAS-Cog11 score will include treatment, timepoint, treatment-by-timepoint interaction as the fixed effects and baseline as the covariate. The Model for the co-primary endpoint ADCS-CGIC score will include treatment, timepoint, treatment-by-timepoint interaction as the fixed effects. The variance-covariance matrix will be assumed to be UN.

This analysis will be conducted after all participants have reached Week 12 or early withdrawal, whichever comes first. The primary analysis will be conducted in ITT. The mITT and PPS will be used to support the primary analysis.

Descriptive statistics per visit and change from baseline for each visit will be provided.

As the study is also designed to explore the effectiveness of three buntanetap-treatment dose levels on co-primary endpoints, similar MMRM will be applied comparing each buntanetap-treatment dose arm with placebo.

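### SAP 8.2.3: with two visits TOEPH is UN in another form, and AR(1), if ever reached, misstates the Week 12 standard error when the two visit variances differ

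*SAP*

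**What the plan says.** SAP 8.2.3 sets out one MMRM recipe for the two co-primary endpoints and the secondary endpoints, fitted by REML. The visit term in the model statement has two levels: "V: post-baseline visit (Week 6, Week 12". On the covariance it says: "The Unstructured (UN) variance-covariance structure will be initially used to explore the variance-covariance matrix across visits". If the fit does not converge, "a heterogeneous Toeplitz (TOEPH) as the covariance matrix will be tried first, and then first-order autoregressive (AR(1)) to achieve convergence". On inference it says: "The Kenward-Roger approximation will be used to estimate denominator degrees of freedom". No robust (sandwich) standard error is named. The comparison of pooled buntanetap with placebo is "carried out by means of the contrasts on the treatment factor by visit effect", so the Week 12 standard error drives the test.

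SAP 8.2.7, on the co-primary analysis, names only one structure and no fallback: "The variance-covariance matrix will be assumed to be UN". Protocol 6.8 does the same: "An unstructured covariance matrix will be used and the Kenward-Roger approximation will be used to adjust the denominator degrees of freedom". SAP section 3 gives the SAP precedence over the protocol where they differ, so the SAP 8.2.3 ladder is the operative rule for a failed fit.

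**The concern.** A covariance ladder should step down to simpler structures while keeping inference on the primary contrast sound. Here the first step down does not simplify anything. The second step removes the one feature that the Week 12 standard error depends on, a variance of its own for Week 12.

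Under AR(1) the Week 12 treatment estimate hardly moves, but its standard error is built from a variance averaged over both visits. If Week 12 is the more variable visit, the standard error is too small and the type I error is inflated. If Week 12 is the less variable visit, power is lost. The rule covers ADAS-Cog11, ADCS-CGIC, ADCS-ADL, DSST and the dose-level versions of these models.

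**Working it through.** **Inputs from the SAP.** Two post-baseline visits (8.2.3). 210 pooled active versus 70 placebo, difference 2.7, SD 6.0, two-sided 5%, 12.5% dropout (section 6).

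**Assumptions.** The planned SD of 6.0 is taken as the Week 12 SD. The documents give no Week 6 SD and no between-visit correlation, so a range is shown for the first and a value is assumed for the second.

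**Step 1: the plan's own figure.** The SAP states: "A sample size of 280 (210 combining all three buntanetap-treatment groups and 70 in control) will have 90% power to detect a treatment difference".
- Standard error = 6.0 × √(1/70 + 1/210) = 0.828.
- Power = Φ(2.7/0.828 − 1.960) = Φ(3.261 − 1.960) = 90.3%, or 90.1% with the t distribution.
- 280/(1 − 0.125) = 320.

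The plan's figures reproduce.

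**Step 2: parameter count for two visits.**
- UN: two variances and one covariance, 3 parameters.
- TOEPH: two variances and one correlation, 3 parameters. The covariance equals correlation × SD6 × SD12, so each TOEPH matrix is a UN matrix and the reverse.
- AR(1): one variance and one correlation, 2 parameters.

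**Step 3: the AR(1) standard error.** With complete data the single AR(1) variance is about (SD6² + SD12²)/2. Hence:
- ratio of AR(1) to correct Week 12 standard error = √((SD6² + 36)/72)
- actual two-sided type I error = 2 × (1 − Φ(1.96 × ratio))
- power = Φ(3.261 − 1.96 × ratio)

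For Week 6 SD 5: ratio = √(61/72) = 0.920, standard error = 0.762, type I error = 2 × (1 − Φ(1.804)) = 7.1%. For Week 6 SD 7: ratio = √(85/72) = 1.087, power = Φ(3.261 − 2.130) = 87.1%.

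| Assumed Week 6 SD | Ratio | AR(1) standard error | Type I error |
|---|---|---|---|
| 4 | 0.85 | 0.704 | 9.6% |
| 5 | 0.92 | 0.762 | 7.1% |
| 5.5 | 0.96 | 0.794 | 6.0% |
| 6 | 1.00 | 0.828 | 5.0% |
| 7 | 1.09 | 0.900 | 3.3% |
| 8 | 1.18 | 0.976 | 2.1% |

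The ratio depends only on SD6/SD12, not on arm sizes. The same type I errors therefore hold for the other two-visit endpoints and the dose-level models at the same SD ratio.

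**Step 4: simulated REML fits.** Settings: 80 versus 240 randomized, 12.5% missing at Week 12, Week 12 SD 6.0, correlation 0.5, 1,000 trials per row.

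| Week 6 SD | Mean standard error, UN / AR(1) | Rejection under the null, UN / AR(1) |
|---|---|---|
| 6 | 0.815 / 0.815 | 4.4% / 4.5% |
| 5 | 0.813 / 0.744 | 4.8% / 7.7% |
| 4 | 0.816 / 0.685 | 4.9% / 9.3% |
| 7 | 0.815 / 0.893 | 5.4% / 3.4% |

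In all 4,000 trials UN and TOEPH gave the same −2 REML log-likelihood to within 2e-8 and the same Week 12 standard error to within 3e-6. Both converged every time. Monte Carlo error on the rejection rates is about 0.7 points. These fits used a fixed t cutoff (1.968), not Kenward-Roger.

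**Step 5: which endpoints.** The schedules of events (Protocol Appendix 1, SAP Appendix 1) show ADAS-Cog11, ADCS-CGIC, ADCS-ADL and DSST at both Week 6 and Week 12. MMSE has no Week 6 assessment, so it has no two-visit covariance to model.

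**The case against.** The strongest reply is that AR(1) will almost certainly never be used. A three-parameter covariance with about 280 participants is easy to fit, and UN converged in every simulated trial. SAP 8.2.7 and Protocol 6.8 both commit to UN. This stands, and it keeps the point minor. It does not remove it, because a fallback is written only for the rare case and should be sound there.

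A reader might infer that the ladder, as written, yields a wrong standard error or p-value. The documents do not support that. Three things are needed: UN fails, TOEPH fails, and the two variances differ. With equal variances AR(1) is correct.

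A reader might also infer that the error must inflate the type I error, on the view that change scores spread out over time. The documents give one SD per endpoint and nothing for Week 6, so neither direction nor size can be read from them. The argument is also less direct for ADCS-CGIC, a bounded 1 to 7 rating that is not analyzed as a change from baseline.

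A third tempting reading is that every tested secondary endpoint is affected. MMSE is not.

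Finally, TOEPH is not useless. Fitting the same model in another parameterization can rescue a failed optimization, and the recommended first step relies on exactly that. What stands is only that TOEPH is not a simpler model, so it should be described as a second attempt at UN.

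**Conclusion.** The point holds in conditional form, as a low-cost improvement to the SAP. That TOEPH equals UN for two visits, and that AR(1) imposes equal variances, is algebra and needs no assumption.

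The consequence rests on both three-parameter fits failing and on a Week 6 SD that the documents do not give. Under those conditions, with Week 12 SD 6.0, the actual type I error ranges from 9.6% (Week 6 SD 4) through 5.0% (SD 6) to 2.1% (SD 8). At SD 7 power falls from 90% to 87%. The point covers ADAS-Cog11, ADCS-CGIC, ADCS-ADL, DSST and their dose-level models. It is no reason to doubt a result obtained from a converged UN fit.

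**What to change.** Replace the ladder in SAP 8.2.3 with the following rule, and make SAP 8.2.7 refer to it.

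1. If UN does not converge, refit the same unstructured model with another parameterization (TOEPH or Cholesky), supplied starting values or a different scoring method. State that these are the same model.
2. If that also fails, do not use AR(1) with model-based standard errors. Prespecify one of two options:
   - AR(1) with empirical (sandwich) standard errors and a named degrees-of-freedom method in place of Kenward-Roger; or
   - a Week 12 ANCOVA with baseline as covariate (for ADCS-CGIC, a Week 12 comparison of groups).

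The cost is SAP wording only. The downside lies with the Week 12-only option: it drops the Week 6 data of participants who discontinue, and so gives up some of the protection that the MMRM offers under the missing-at-random assumption in SAP 8.8. The sandwich option keeps those data.

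### The MMRM fits one baseline slope to Week 6 and Week 12; a baseline-by-visit term would guard, at almost no cost, against a small loss of precision and, under specific dropout patterns, a small shift at Week 12

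*SAP*

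**What the plan says.** SAP section 8.2.3 gives the mean model for ADAS-Cog11 and the secondary endpoints as "intercept + Base + T + V + T*V", where the visit factor has the levels Week 6 and Week 12. SAP section 8.2.7 repeats it in words for the primary analysis: "treatment, timepoint, treatment-by-timepoint interaction as the fixed effects and baseline as the covariate". SAP section 8.6 and Protocol section 6.8 likewise enter baseline as a plain covariate. Neither document adds a baseline-by-visit term or plans a sensitivity model that contains one.

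Two endpoints fall outside the point. The ADCS-CGIC model has no baseline term. MMSE is not scheduled at Week 6 (Appendix 1 of both documents), so there are not two visit-specific slopes to separate. The endpoints concerned are ADAS-Cog11, ADCS-ADL and DSST.

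**The concern.** Week 12 is the primary time point, and ADAS-Cog11 is one of two co-primaries that must both succeed. If the relation between baseline and change is not the same at 6 and 12 weeks, a single slope is a compromise that fits neither visit exactly. That leaves some removable residual variance at Week 12. It also enters the model's implicit prediction of Week 12 for participants who have only a Week 6 value, and so the conditioning on which the missing-at-random assumption in SAP section 8.8 rests. The sensitivity analyses in section 8.8 refit the same MMRM, so no planned fit relaxes the common slope.

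**Working it through.** **1. The plan's own figure.** SAP section 6 states: "210 combining all three buntanetap-treatment groups and 70 in control"; "at a two-sided significance level of 0.05, assuming a delta of 2.7 between the treatment"; "and a common standard deviation (SD) of 6.0"; "will have 90% power to detect a treatment difference".

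- SE = 6.0 × √(1/210 + 1/70) = 0.828.
- 2.7 / 0.828 = 3.26, and Φ(3.26 − 1.96) = Φ(1.30) = 0.903. The stated 90% reproduces.
- 280 / (1 − 0.125) = 320, which agrees with "to account for an expected 12.5% dropout rate".

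This is a two-sample calculation with no baseline or visit term, so the point below does not alter it.

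**2. When the contrast can move.** Let b6 and b12 be the true slopes of change on baseline and b the fitted common slope. To a first approximation, the misfit adds to the Week 12 contrast

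(b12 − b) × (mean baseline of active participants observed at Week 12 − the same mean for placebo).

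The first factor is zero if the slopes are equal. The second has expectation zero under randomization with complete data, and also when dropout depends on baseline identically in every arm. Both factors must be non-zero for a shift, and its sign is the product of their signs.

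**3. Size, by simulation.** Both models were fitted to the same simulated data with an unstructured 2×2 covariance. From the documents: N = 320, 3:1 pooled active to placebo, Week 12 effect 2.7, Week 12 SD of change 6.0, about 12% dropout. Assumed, because the documents do not give them: baseline SD 8, Week 6 SD 5, Week 6 effect half of Week 12, residual correlation 0.6, half of the dropout before Week 6, and the slopes. There were 3,000 trials per scenario. The shift is the common-slope estimate minus the `Base*V` estimate, in ADAS-Cog11 points.

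| Dropout pattern | Slopes −0.10/−0.10 | Slopes −0.10/−0.20 | Slopes −0.05/−0.25 |
|---|---|---|---|
| None | 0.000 | 0.000 | 0.003 |
| Depends on baseline, same in all arms | 0.000 | 0.001 | −0.001 |
| Same dependence, 7% placebo vs 14% active | 0.000 | 0.041 | 0.082 |
| Dependence in active arms only | 0.000 | 0.066 | 0.137 |
| Opposite dependence in active and placebo | 0.001 | 0.138 | 0.273 |
| SE ratio, common slope / `Base*V` | 0.998-1.000 | 1.003-1.005 | 1.016-1.019 |

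With slopes −0.10/−0.40 the SE was 3-4% larger, and the largest shift seen, again with opposite dependence, was about 0.4 points.

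A separate set of 1,500 trials per scenario (80 per arm, change SDs 5.2 and 5.8) agrees:

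- Slopes −0.05/−0.20: mean SE 0.7911 vs 0.7830, a cut of 0.0081 / 0.7911 = 1.0%.
- Slopes −0.10/−0.30: mean SE 0.7962 vs 0.7814, a cut of 0.0148 / 0.7962 = 1.9%.
- Slopes −0.05/−0.10: a cut below 0.1%.
- Active-only dropout dependence, with slopes −0.05/−0.10, −0.05/−0.20 and −0.10/−0.30: effect sizes 2.676 vs 2.704, 2.584 vs 2.665 and 2.597 vs 2.707. The differences are 0.03, 0.08 and 0.11 points.

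**4. Direction.** In one simulated dataset of 150,000 participants with slopes −0.05/−0.20 and active-only dependence, the shift was 0.14 points one way when severe participants left and 0.17 the other way when mild ones did. Reversing the sign of the slopes reversed the direction.

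**5. Scale.** 0.17 / 2.7 = 6% of the planned effect, and 0.17 / 0.828 = 0.21 of the planning SE.

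**The case against.** A common slope is a legitimate pre-specified model and is stated consistently in both documents. Nothing in them shows that the slope changes between Weeks 6 and 12, and regression to the mean alone would affect both visits alike. With complete data, randomization keeps the contrast unbiased under either model. The precision at stake is small.

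Missing data are also partly covered. The control-based imputation in SAP section 8.8 uses baseline, Week 6 and Week 12 jointly, which as described does not force one slope on both visits. Participants who leave after Week 9 are to have an end-of-trial visit with ADAS-Cog11 (Protocol section 4.2 and Appendix 1), so fewer may lack a late value than a flat 12% implies. The simulations used maximum likelihood, with normal critical values for the tests, rather than REML with Kenward-Roger. At this sample size that should matter little for comparing two mean models.

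All of this limits the size of the point and stands. It does not show a disadvantage of the extra term. The imputation analysis is control-based, so it changes the missing-data assumption as well and cannot isolate the effect of the common slope.

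A reader might infer that the primary analysis is biased whenever sicker participants leave more often, or that it understates the effect. Neither follows: the same dependence in every arm gives no shift, and the sign is set by the assumed slopes and dropout pattern.

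**Conclusion.** The model does constrain the baseline slope to be equal at both visits, and relaxing it is a sound minor improvement. If the slopes differ moderately, the Week 12 SE is about 0-2% larger than necessary; if they differ greatly, 3-4%. A shift of roughly 0.03-0.17 points, in either direction, needs moderately unequal slopes together with a dropout rate or dropout-baseline relation that differs between arms. With equal slopes there is no gain, and the extra term raised the SE by at most about 0.2%.

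The slopes, baseline SD and dropout patterns are assumptions. Protocol section 5.1 mentions a tendency, without a definitive pattern, towards more adverse events at higher doses. That makes unequal dropout conceivable but does not establish it.

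The most adverse simulations might tempt a stronger reading. With slopes −0.05/−0.25 and opposite-direction dropout, power was 0.87 vs 0.94 and type I error 6.9% vs 5.4%. That combination is constructed and nothing in the documents points to it. In the other scenarios of the table, type I error for the planned model was 4.5-5.8%. The sample-size statement stands.

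**What to change.** Before unblinding, append `Base*V` to "intercept + Base + T + V + T*V" for ADAS-Cog11, ADCS-ADL and DSST, and align SAP sections 8.2.3, 8.2.7 and 8.6. Leave the ADCS-CGIC and MMSE models as they are. If the sponsor prefers not to alter the primary model, pre-specify the extended model as a sensitivity analysis.

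The cost is one parameter per model and a short amendment; no new data are needed. SAP section 8.9 says the interim sample-size re-estimation has already been done, so the amendment should be dated and should record that those making the change were blinded to the interim results. SAP version 2.0 already amended the handling of missing ADAS-Cog11 items, so a change of this size is practicable.
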